NCT03196167

Sugammadex and Decreased Time to Extubation

Study Protocol

6/19/2020

HRP-503B – BIOMEDICAL RESEARCH PROTOCOL
(2016-1)

Protocol Title: Efficacy and Safety of Sugammadex (2mg/kg) to shorten time-to-extubation among postoperative ICU patients following Aortic Valve Replacement, CABG surgery, or Aortic Valve Replacement with CABG surgery- a prospective randomized placebo- controlled trial.

Principal Investigator: [name].

Protocol Version Number and/ or Date: Version5, June 1, 2020

(If applicable) Clinicaltrials.gov Registration #: NCT03196167

INSTRUCTIONS

This template is intended to help investigators prepare a protocol that includes all the necessary information needed by the IRB to determine whether a study meets approval criteria. **Read the following instructions before proceeding:**

1. Use this protocol template for a PI initiated study that includes direct interactions with research subjects. Additional templates for other types of research protocols are available in the system Library.
2. If a section or question does not apply to your research study, type “Not Applicable” underneath.
3. Once completed, upload your protocol in the “Basic Information” screen in IRES IRB system.

SECTION I: RESEARCH PLAN

1. **Statement of Purpose:** State the scientific aim(s) of the study, or the hypotheses to be tested.
To demonstrate faster time to extubation after arrival in the cardiothoracic ICU in patients undergoing Aortic Valve Replacement (AVR), Coronary Artery Bypass Graft (CABG), or AVR/CABG combination surgery who receive study drug (Sugammadex 2mg/kg) as compared to placebo.
2. **Probable Duration of Project:** State the expected duration of the project, including all follow-up and data analysis activities.
Approximately 36 months
It is estimated that 3 subjects will be randomized per week allowing for data collection to be completed in 2 years for study start-up, with an additional 12 months for data analysis.
3. **Background:** Describe the background information that led to the plan for this project. Provide references to support the expectation of obtaining useful scientific data.

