If a patient fails the 30 minute CPAP criteria, the ICU intensivist will be immediately notified. Every attempt will be made to correct the underlying cause of CPAP failure, and a prompt reassessment will be made as deemed appropriate by the intensivist to reattempt CPAP versus continuing controlled mechanical ventilation.

It is estimated conservatively that the study personnel will randomize 3 patients per week allowing for data collection to be completed within 1 year of study commencement. Data analysis and dissemination of findings will be conducted over the subsequent 6 months by the study institution investigators per the publication plan below.

Blinded analyses of the data will be performed by the study investigators along with the departmental statistician in the Department of Anesthesiology at the Yale School of Medicine.

**Variables/Time Points of Interest:** The primary outcome is the time to extubation, which will be the duration from arrival to the ICU to the extubation time. Participants' blood pressure, heart rate, and chest tube output will be tracked from arrival to the CTICU until extubation per ICU protocol.

**Statistical Methods:** Baseline comparability. We expect that the randomization process will produce reasonably comparable groups. However, the adequacy of the randomization will be assessed by comparing the distribution of baseline demographic and clinical characteristics among the intervention groups. Comparability for continuous variables will be examined graphically and by summary statistics (means, medians, quartiles, etc.). Categorical variables will be examined by calculating frequency distributions.

**Proposed statistical test/analysis:** Positively skewed variables will be log-transformed prior to hypothesis testing. For the primary outcome, a two-sided Student's t-test will be used to compare the time to extubation between the two groups. If necessary, covariate adjustment will be made using the multiple linear regression analysis method. Differences between means and 95% confidence intervals will be estimated to describe the magnitude of intervention difference between the two groups. As part of sensitivity analyses, the time-to-extubation outcome will be also analyzed by the Cox regression model. To compare the categorical adverse events between two groups, chi-square test or Fisher's exact test will be used.

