**Missing Data:** Prevention is the most obvious and effective manner to control bias and loss of power from missing data. Therefore, several strategies (e.g., timely data entry and daily missing data report) will be imposed to limit the likelihood that missing data will occur during this study. This protocol will follow the intention to treat principle, requiring follow-up of all subjects randomized regardless of the actual treatment received.

**Power analysis:** Our 'in-house' historical data ( $n = 73$ ) showed that after excluding outliers greater than the 80th percentile, patients undergoing isolated CABG demonstrated a mean of 8.39 hours to extubation (SD 2.89). Although we anticipate a Hawthorne effect demonstrating reduced time to extubation in both the active and placebo arms of the present study, we have conservatively chosen to maintain power based on historical data. We therefore estimate that 45 subjects per group will give us 90% power to detect a clinically relevant effect size of 2-hours difference between active and placebo groups at an alpha value of 0.05 using a two-sided two-sample t-test. To allow for post consent, pre-randomization study drop out, we will aim to enroll a total of 110 ( $90 + 20 = 110$ ) subjects.

Per-protocol Sensitivity Analysis: In parallel with the primary analysis, if exclusions above occur post randomization but prior to drug administration, the investigators will conduct a parallel "per-protocol" sensitivity analysis.

Drug supplies will be supplied by the sponsor.

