**Adverse Experience Reporting:** Throughout the duration of the study, researchers will adhere to good clinical practice and the guidelines of the institution. Patient vitals will be continuously monitored during and after the administration of the test drug. A data and safety monitoring board (DSMB) consisting of the head nurse and a senior critical care staff will meet monthly to discuss any serious events. Any incidence of anaphylaxis or unexplained hypotension requiring initiation of pressors or cardiac pacing within 5 minutes of drug administration will be reported and evaluated. Increases in chest tube output considered clinically significant by the critical care team will be noted. Any of these adverse events will trigger an analysis by the DSMB. If the DSMB determines that study drug may be causing an increase in adverse events, the study will be suspended until the DSMB is able to fully review the events and make a recommendation in consultation with the Yale Human Investigations Committee. The local Merck research

representative will also be notified about the events. If the data monitoring board and/or institutional review board (IRB) view that the study is unsafe, the study will be discontinued.

**Specific Safety Events to Be Reported During Manuscript Preparation:** For manuscript preparation, the rates of hypotension, anaphylaxis, and bleeding (i.e. Chest Tube output) will be reported and compared between active and placebo groups.

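### For categorical adverse events the plan names a chi-square or Fisher test, with no rule for choosing and no risk difference or interval; at 45 per arm the result can turn on that choice, and a non-significant p-value says little about safety.

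*SAP*

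**What the plan says.** The protocol title names both aims: "Efficacy and Safety of Sugammadex (2mg/kg) to shorten time-to-extubation". The Statement of Purpose, however, concerns time to extubation only.

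For events, the SAP (Proposed statistical test/analysis) has one sentence. It opens "To compare the categorical adverse events between two groups" and names a chi-square or Fisher's exact test, and nothing else. Item 13 of the protocol, Statistical Considerations, gives the same method. Neither place says when each test applies, whether a chi-square would be continuity-corrected, or what significance level holds for safety.

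The same paragraph provides for estimation, but of means: "Differences between means and 95% confidence intervals will be estimated to describe the magnitude of intervention difference". No corresponding sentence covers proportions.

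The SAP section on safety events for the manuscript lists hypotension, anaphylaxis and bleeding, the last described as chest tube output. It says their rates "will be reported and compared between active and placebo groups". It names no effect measure and no interval.

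The sample size rests on the primary outcome alone: "45 subjects per group will give us 90% power" for an "effect size of 2-hours difference between active and placebo groups", "at an alpha value of 0.05 using a two-sided two-sample t-test". No event rate and no power for safety is given.

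**The concern.** A trial sized for a 2-hour difference in a continuous outcome will usually be too small to test differences in uncommon events. If the only planned comparison is a test of no difference, its most likely output is a non-significant p-value, whether or not the drug causes an excess of events. An interval would show how large an excess the data leave open, and that is the safety question 90 patients can help to answer.

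The plan also permits two tests that can disagree when events are few, and gives no rule for choosing. Whether an imbalance is called significant could then depend on a decision made after the table is seen.

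**Working it through.** **Inputs.** From the SAP power analysis: 45 per arm, difference 2 hours, SD 2.89 hours, two-sided alpha 0.05. No alpha is stated for safety, so 0.05 two-sided is assumed. No event rates are given, so all rates below are assumptions, shown over a range.

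**Step 1: the plan's own figure.** Standardised difference = 2 / 2.89 = 0.692. Noncentrality = 0.692 × √(45/2) = 3.283 on 88 degrees of freedom. The two-sided t-test then has power 0.901, so the stated 90% is reproduced. It applies only to extubation time.

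**Step 2: one table, three p-values.** Take 5/45 against 0/45, that is, 5 events and 85 non-events in 90 patients.

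- Fisher, two-sided: 2 × C(45,5) / C(90,5) = 2 × 1,221,759 / 43,949,268 = 0.056.
- Uncorrected chi-square: 90 × (5×45 − 40×0)² / (45×45×5×85) = 5.29, p = 0.021.
- Yates-corrected chi-square: 90 × (225 − 45)² / (45×45×5×85) = 3.39, p = 0.066.

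The expected event count is 5 × 45/90 = 2.5 per arm. That is below the usual threshold of 5, so Fisher is the conventional choice, but the plan does not say so. Against zero events in the other arm, significance needs 6 events by Fisher (p = 0.026) or Yates (p = 0.035), but only 4 by the uncorrected chi-square (p = 0.041).

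**Step 3: power at 45 per arm.** Power is the sum, over all pairs of counts (i, j) with i > j and p < 0.05, of Bin(i; 45, p₁) × Bin(j; 45, p₀).

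| Assumed rates | Fisher | Uncorrected chi-square |
|---|---|---|
| 10% v 5% | 6% | 16% |
| 10% v 2% | 15% | 39% |
| 20% v 10% | 18% | 28% |
| 15% v 5% | 23% | 39% |
| 20% v 5% | 48% | 63% |
| 11.1% v 0% | 38% | 75% |

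Fisher's test stays below 50% in every row. The uncorrected chi-square comes near conventional power only in the last row, where the comparator rate is exactly zero.

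**Step 4: what an interval would show.** The Newcombe interval combines the Wilson limits of each arm.

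- For 5/45 (0.111) the Wilson limits are 0.048 and 0.235; for 0/45 they are 0 and 0.079.
- Lower limit: 0.111 − √[(0.111 − 0.048)² + (0.079 − 0)²] = 0.011.
- Upper limit: 0.111 + √[(0.235 − 0.111)² + (0 − 0)²] = 0.235.
- The risk difference is therefore 11.1 points, 95% interval 1.1 to 23.5.

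For 4/45 against 2/45, Fisher gives p = 0.68. The risk difference is 4.4 points, with a Newcombe interval from −7.2 to 16.7. The p-value alone hides that an excess of up to 16.7 points remains compatible with the data. Even 0/45 in an arm allows a true rate up to 1 − 0.025^(1/45) = 7.9%.

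**The case against.** Five points can be made for the plan.

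- **A reader might infer that 5 against 0 is non-significant under this plan.** The documents do not support that, because the uncorrected chi-square, which the plan allows, gives 0.021. What stands is that the answer depends on an unspecified choice.
- **A reader might also infer that the investigators will treat non-significance as proof of safety.** No text says so, and no safety hypothesis is stated. The risk of such a reading remains, since safety is in the title and no other comparative measure is planned.
- **Rates by arm will be reported, so anyone can derive an interval.** This is true, and it supplies half of the remedy. It does not make the interval the prespecified result.
- **Protection of participants does not depend on a p-value.** Listed events trigger review by the monitoring board, and the study can be suspended or discontinued (protocol item 12; SAP, Adverse Experience Reporting). That stands, but it concerns conduct during the trial, not the final comparison.
- **Not every safety measure is binary.** Chest tube output may be analysed as continuous, and the sentence on differences between means could then cover it. The point is therefore limited to categorical events.

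Setting Fisher's p-value beside a Newcombe interval also mixes a conservative method with a less conservative one. For 5 against 0 the conditional exact interval for the odds ratio runs from 0.96 to infinity and includes no effect. A remedy that left the interval method open would repeat the fault, so one method must be named.

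**Conclusion.** The point holds for categorical adverse events. The plan names only a test, does not say which one, and specifies no effect estimate or interval. For 5 against 0 at 45 per arm, the permitted tests give p-values from 0.021 to 0.066, on both sides of 0.05. Under the assumed rate pairs, power runs from 6% to 48% by Fisher and from 16% to 75% by uncorrected chi-square. These figures rest on 45 analysed per arm, two-sided 0.05 for safety, and rates that the documents do not supply.

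A non-significant safety test in this trial would carry little information. The documents do not show that the sponsor intends to claim safety from one. The primary analysis is unaffected. This is a cheap improvement to the analysis and reporting of an aim that the title names.

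**What to change.** Amend item 13 of the protocol and two SAP sections: Proposed statistical test/analysis, and Specific Safety Events to Be Reported During Manuscript Preparation.

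1. For each named binary event, report the count and percentage per arm (the rates are already planned). Make the risk difference with a Newcombe 95% interval the main comparison, and quote its upper limit in the text.
2. State whether bleeding is analysed as a binary event or as continuous chest tube output. If continuous, report the difference in means with its 95% interval.
3. If p-values are kept, use Fisher's exact test throughout and label them descriptive. Say in advance that the interval is the main result, because the two can disagree, as they do for 5 against 0.
4. State that a non-significant test is not evidence of safety.

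The cost is SAP and protocol wording and a few lines of code, with no extra data or patients. The downside is a more modest safety statement in the report.

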4. Determination that the patient will require prolonged mechanical ventilation possibly requiring muscle relaxation based on the intraoperative course and clinical judgment of the study PI or collaborating intensivists.
5. Intraoperative hypoxia or on arrival to the ICU. (Please see Study Flowchart).
6. Cardiac arrest
7. Sudden arrhythmia (Ventricular tachycardia runs/sudden bradycardia with improper pacemaker detection/function) precluding fast-track extubation protocol.
8. Need for two or more inotrope initiation precluding fast-track protocol. Only a single vasopressor/inotrope may be initiated without excluding the subject.
9. Postoperative ST changes.

10. A positive standard of care pregnancy test during your pre-operative evaluation

9. How will **eligibility** be determined, and by whom?

Eligibility at pre-op and post-op will be based on protocol specific inclusion and exclusion criteria and will be determined by the PI or Sub-I's in collaboration with the ICU attending physician

10. **Risks:** Describe the reasonably foreseeable risks, including risks to subject privacy, discomforts, or inconveniences associated with subjects participating in the research.

Sugammadex is generally safe and well tolerated. Potential risks associated with sugammadex are: hypersensitivity, including anaphylaxis/anaphylactic shock – previous trials suggest this risk is small. Cardiac arrhythmias including bradycardia & tachycardia where intervention is rare and responsive to usual treatment. Other reported risks include nausea, vomiting, constipation.

Bleeding was originally thought to be a side effect, but studies have since showed that Sugammadex falsely elevates the PTT without increasing bleeding risk. (see reference on last page.)

11. **Minimizing Risks:** Describe the way the above-mentioned risks will be minimized.

Patients will all be in a critical care environment and monitored very closely including: blood pressure, heart rate, and chest tube output will be tracked from arrival to the CTICU until extubation per ICU protocol. Subtle changes in the patient's hemodynamic status are easily seen and treated if necessary.

12. **Data and Safety Monitoring Plan:** Include an appropriate Data and Safety Monitoring Plan (DSMP) based on the investigator's risk assessment stated below. (Note: the HIC will make the final determination of the risk to subjects.)

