- e.) Unrelated: Adverse event is clearly not related to investigational procedures(s)/agent(s).

4. Plan for Grading Adverse Events:

The following scale will be used in grading the severity of adverse events noted during the study:

1. Mild adverse event
2. Moderate adverse event
3. Severe

5. Plan for Determining Seriousness of Adverse Events:

Serious Adverse Events:

In addition to grading the adverse event, the PI will determine whether the adverse event meets the criteria for a Serious Adverse Event (SAE). An adverse event is considered serious if it results in any of the following outcomes:

1. Death;
2. A life-threatening experience in-patient hospitalization or prolongation of existing hospitalization;
3. A persistent or significant disability or incapacity;
4. A congenital anomaly or birth defect; OR

5. Any other adverse event that, based upon appropriate medical judgment, may jeopardize the subject's health and may require medical or surgical intervention to prevent one of the other outcomes listed in this definition.

An adverse event may be graded as severe but still not meet the criteria for a Serious Adverse Event. Similarly, an adverse event may be graded as moderate but still meet the criteria for an SAE. It is important for the PI to consider the grade of the event as well as its "seriousness" when determining whether reporting to the IRB is necessary.

Only the following adverse events will be tracked. These AE's will trigger an immediate DSMB review; any incidence of anaphylaxis; unexplained hypotension requiring initiation of pressors; cardiac pacing within 5 minutes of drug administration; tachycardia, bradycardia or onset of atrial fibrillation; or increases in chest tube output considered clinically significant by the critical care team. The DSMB will be notified within 2 business days of determination by telephone or email. A written report will be provided within 7 days of the determination. Any incidents meeting SAE criteria will be reported per the IRB reporting policy.

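### Protocol and SAP differ on whether the 5-minute window limits hypotension, the planned between-arm comparison of hypotension names no definition, and rises in a running pressor are not counted

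*SAP*

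**What the plan says.** **Protocol, Section I, item 12.c.5 (Plan for Determining Seriousness of Adverse Events).** The event list opens with "Only the following adverse events will be tracked". It then separates its entries by semicolons: "unexplained hypotension requiring initiation of pressors; cardiac pacing within 5 minutes of drug administration; tachycardia, bradycardia or onset of atrial fibrillation". Listed events trigger an immediate DSMB review.

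**SAP, Adverse Experience Reporting.** The corresponding sentence joins the two events with a conjunction and no punctuation: "unexplained hypotension requiring initiation of pressors or cardiac pacing within 5 minutes of drug administration will be reported and evaluated". These events also trigger a DSMB analysis, and the study can be suspended as a result.

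**SAP, Specific Safety Events to Be Reported During Manuscript Preparation.** The planned comparison is stated as "the rates of hypotension, anaphylaxis, and bleeding (i.e. Chest Tube output) will be reported and compared between active and placebo groups". It gives no time window and no pressor condition, and it does not refer back to the trigger sentence. The test is given under Proposed statistical test/analysis: "To compare the categorical adverse events between two groups, chi-square test or Fisher's exact test will be used".

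**Observation period.** Under Variables/Time Points of Interest the SAP says "Participants' blood pressure, heart rate, and chest tube output will be tracked from arrival to the CTICU until extubation per ICU protocol".

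**Pressors at randomisation.** The protocol's pre-randomisation exclusions (Section I, item 8, eighth entry) state "Only a single vasopressor/inotrope may be initiated without excluding the subject". The SAP's Protocol Amendments (third change) record that low-dose pressor infusions were permitted if they did not preclude the fast-track pathway.

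**The concern.** Hypotension is one of three safety events that the SAP will compare by arm, and it is one of the events that bring the DSMB in. If the protocol list is followed, a qualifying episode counts whenever it occurs after dosing. If the SAP sentence is followed on its natural reading, an episode counts only in the first 5 minutes. Because the protocol tracks listed events only, the choice of wording affects what is recorded as an adverse event as well as what is tabulated. Someone preparing the safety table could defend either count, and nothing in the plan fixes the choice before the data are seen.

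A second gap is common to both documents. Each requires that a pressor be started. In a patient who arrives at randomisation on one agent, hypotension managed by increasing that agent meets neither wording. Such patients are allowed in the trial, and the plan does not say how they contribute to the comparison.

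**Working it through.** **1. The plan's own figure.** No document states a hypotension rate, so the only figure to reproduce is the sample size (SAP, Power analysis). With a difference of 2 h, SD 2.89 h, two-sided alpha 0.05 and 90% power, the two-sample t-test needs 44.86 per group, rounded up to 45; power at 45 is 90.1%. The stated 45 reproduces. It is used below only as the arm size.

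**2. The texts side by side.**

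| | Window on pacing | Window on hypotension |
|---|---|---|
| Protocol list | 5 minutes | none |
| SAP sentence, natural reading | 5 minutes | 5 minutes |
| SAP sentence, pacing-only reading | 5 minutes | none |
| SAP comparison sentence | not applicable | not stated |

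The SAP sentence also allows pacing to be read as something that the hypotension required, and so not as an event in its own right. The protocol's semicolons rule that out.

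**3. How much the window could matter.** Assumptions, none of them from the documents: dosing 0.5 to 1.0 h after ICU arrival; a rate P of 5% to 30% from dosing to extubation; constant hazard. Extubation is put at the historical mean of 8.39 h (SAP, Power analysis).

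- Time from dosing to extubation: (8.39 − 0.5) × 60 = 473.4 min, or (8.39 − 1.0) × 60 = 443.4 min.
- Share taken by 5 minutes: 5/473.4 = 1.06%, or 5/443.4 = 1.13%. The open window is about 95 or 89 times as long.
- Rate within 5 minutes: 1 − (1 − P)^(5/T), with T in minutes.

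| Assumed P | Events in 45, open window | Events in 45, within 5 min |
|---|---|---|
| 5% | 2.25 | 0.024 to 0.026 |
| 10% | 4.5 | 0.050 to 0.053 |
| 20% | 9.0 | 0.106 to 0.113 |
| 30% | 13.5 | 0.169 to 0.181 |

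**4. Unequal exposure if counting runs to extubation.** Suppose that the active arm is extubated 2 h sooner (6.39 h) at the same hazard, with dosing at 0.5 h. Its rate is 1 − (1 − P)^(5.89/7.89). For P from 5% to 30% this gives 1.7 to 10.5 events in 45, against 2.25 to 13.5 on placebo. The difference comes only from shorter exposure.

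**5. The opposite direction.** Suppose that the drug causes an acute reaction in 15% of active patients within 5 minutes and placebo has none: 0.15 × 45 = 6.75, taken as 7. Fisher's exact test on 7/45 against 0/45 gives p = 0.012. Now add a background rate b up to extubation, equal in both arms. The active rate becomes 1 − 0.85 × (1 − b).

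- b = 10%: 11 against 4, p = 0.087 (placebo expectation 4.5; taking 5 gives p = 0.17).
- b = 20%: 14 against 9, p = 0.33.
- b = 30%: 18 against 14, p = 0.51 (placebo expectation 13.5; taking 13 gives p = 0.38).

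A short window can miss later events; a long one can dilute an acute effect.

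**The case against.** A reader might infer that the compared hypotension rate has two stated definitions, one in each document. The documents do not support that. The comparison sentence stands under its own heading and adopts neither trigger text. Both 5-minute phrases define what is reported and what brings in the DSMB. They become candidate definitions only by inference, chiefly because the protocol tracks listed events alone. This objection stands: the compared outcome is undefined.

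A reader might also take the SAP as plainly limiting hypotension to 5 minutes and conclude that most events would go uncounted. The sentence can be read with the window on pacing only, and it then agrees with the protocol. Even on the natural reading, losing most events requires that the trigger be used as the outcome and that events not cluster after dosing. A constant hazard suits background hypotension better than a reaction to a single dose. Blood pressure is tracked until extubation in any case, so the raw data for a longer window are planned. These limits stand.

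On pressors, both documents use the same condition, so there is no contradiction between them, and starting a second agent after randomisation would still count. The number of patients on a pressor at dosing is not given, so this gap cannot be sized. It remains a gap in the count.

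The objections do not remove the need for a definition. The two trigger texts do not clearly agree, a test between arms is planned, and the outcome to be tested has neither a criterion nor a window.

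**Conclusion.** The concern holds as a problem of outcome definition and of agreement between the two documents. The protocol puts no time limit on hypotension; the SAP most naturally puts 5 minutes on it but can be read otherwise; the planned comparison does not say which applies. Hypotension managed by increasing a pressor already running is counted under neither wording.

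The size is illustrative only and rests on the assumed rates, the assumed dosing time and the constant hazard. Under them the open-window count is roughly 75 to 95 times the 5-minute count (13.5/0.181 = 75; 2.25/0.024 = 94), and early clustering would reduce that ratio. The direction of any distortion is not known in advance: the choice of window could hide a signal or create one.

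The correction should be made because hypotension is both a compared safety outcome and a DSMB trigger. It does not touch the primary outcome, the 45 per group or the 90% power.

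**What to change.** 1. Reconcile the protocol's event list (Section I, item 12.c.5) and the SAP's Adverse Experience Reporting to one wording that shows which events the 5-minute window governs and whether pacing is an event in its own right.
2. In the SAP, next to the comparison of safety rates, define one hypotension outcome by criterion, start and end of counting. Count it over the same fixed post-dose window in both arms. If it is counted to extubation instead, adjust for exposure time, for example by comparing events per patient-hour, because the drug is expected to shorten that time.
3. Report the within-5-minute subset separately.
4. For outcome counting only, also record unexplained hypotension that leads to an increase of a pressor already running, as a separate category. The clinical criterion is for the investigators to settle.
5. Fix these choices before treatment codes are opened.

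Cost: mainly wording, plus somewhat more events to record and review. Tracking is planned only to extubation. On the described pathway (10 minutes after dosing, then a 30-minute CPAP trial) extubation comes no sooner than 10 + 30 = 40 minutes after dosing. A fixed window longer than that may need blood pressure data after extubation for some patients.
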